1.2 Rationale

In-vitro, the been shown to significantly inhibit the growth of *Malassezia species* most frequently associated with TV and Seborrheic Dermatitis. Based on these observations, topical application of the investigational product (IP) probiotic DBI-002 could treat TV and other skin diseases associated with an increased abundance of *Malassezia*

species.

2 POTENTIAL RISKS AND BENEFITS

2.1 Potential Risks

the active ingredient in IP probiotic DBI-002, has been reported to be an opportunistic pathogen. Most infections caused by this organism have been **nosocomial** (originating in a hospital) and often as a result of the contamination of hospital equipment or fluids and have occurred in **immunocompromised** hosts (Tena et al., 2015).

It is possible that once daily applications for five consecutive days of IP could could result in a worsening of the TV. It is possible, but unlikely, that the application of IP

could result in a localised infection, cellulitis, or a systemic bacterial infection. For the skin scrub sample collection, phosphate-buffered saline (PBS) with a mild detergent solution will be used and it could cause a local irritant reaction, although also unlikely.

2.2 Potential Benefits

In vitro antibiosis assays performed by DermBiont demonstrated that the strain used in the IP probiotic DBI-002 significantly inhibited the growth of *Malassezia*. It is possible that either a single treatment or once daily applications for five consecutive days of the IP probiotic DBI-002 could result in improvement or even a clinical and microbiologic cure of the subject's TV. It should be noted that if worsening of the TV or more severe disease were to occur, the strain is susceptible to commonly used oral antibiotics as well as topical antimicrobials.

3 STUDY OBJECTIVE AND PURPOSES

The purpose of this study is to evaluate the safety and tolerability of DBI-002 in patients with active TV. Secondly, the purpose is to observe the effect of the IP on the abundance of *Malassezia species*. Thirdly, the purpose is to evaluate presence or persistence of **Malassezia** strain following either a single treatment application or once daily applications for five consecutive days of DBI-002 IP gel. Fourthly, the purpose is to explore any probiotic effect of the vehicle gel. Lastly, the purpose is to observe the effect of DBI-002 on the signs and symptoms of active TV.

4 STUDY DESIGN AND ENDPOINTS

4.1 Description of the Study Design

4.1.1 Study Design/Type

This is a randomized, double-blinded, aqueous gel-controlled, within-patient, comparison trial examining the safety and effect of different doses of DBI-002 probiotic vs. aqueous gel and vehicle gel vs. aqueous gel in patients with Tinea versicolor.

This is a single center Phase 2A clinical trial. The trial includes a Screening and Enrollment period of up to 28 days, a 1-day or 5-day Treatment Period, and a Safety Follow-Up Period to Day 14. Study visits will occur at screening/baseline and on treatment period study days Day 1

if enrolled to receive a single treatment dose, and Days 1, 2, 3, 4, and 5 if enrolled to receive multiple treatment doses. A safety follow-up visit will occur on Day 14 (\pm 2 days). There will be 3-4 scheduled visits for subjects enrolled to receive a single treatment dose, and 6-7 scheduled visits per subject enrolled to receive multiple treatment doses. All treatments will be performed at the investigative site during the study. Subjects meeting the inclusion/exclusion criteria at screening will be enrolled into one of three cohorts of the study. Each of the probiotic cohort groups (Cohorts 1, 2, 3) will enroll approximately 6 subjects. The vehicle gel vs. aqueous gel group (Cohort 4) will enroll approximately 4 subjects.

Each subject will be randomly assigned to have the assigned dose of DBI-002 probiotic, vehicle gel, or aqueous gel applied to the TV-affected skin location (~100 cm²) on their chest or back. Neither the subject nor the evaluating investigator will know to which treatment group each TV-affected skin location has been assigned.

For each of the three probiotic cohorts, the single-treatment subjects (approximately 2) will be enrolled first. After every single-treatment subject has completed the Day 5 visit, local tolerability and adverse events (AEs) will be assessed. If there are no safety signals, enrollment of the cohort's multiple treatment subjects (approximately 4) will begin. After every multiple treatment subject has completed the Day 14 visit, local tolerability and adverse events (AEs) will be assessed. If there are no safety signals, enrollment the next cohort will begin. Cohort 1 must be completed before enrolling Cohort 2. Cohort 2 must be completed before enrolling Cohort 3. If there are safety signals specific to local tolerability and AEs from either of the first two cohorts, the following dose escalating cohort may be not be enrolled if the Investigator and sponsor are in agreement.

Cohort 4 subjects will receive multiple treatments, Enrollment of Cohort 4 is independent of the three probiotic cohorts, meaning that subjects may be enrolled before, in parallel with, or after the probiotic cohorts.

Subjects enrolled to the single-treatment dose groups:

Visit 0 (may be combined with Visit 1): Screening and enrollment visit, KOH test of TV-affected chest and back skin locations

Visit 1: Baseline visit, Urine pregnancy test as applicable, clinical grading of signs and symptoms of TV, randomization of IP or vehicle gel to chest and back, scrub samples and samples for bacterial culture of IP and aqueous gel TV-affected anatomical locations prior to applications, application of IP and aqueous gel, adverse event recording

Visit 2: Clinical grading of signs and symptoms of TV, scrub samples and samples for bacterial culture of IP and aqueous gel TV-affected anatomical locations, clinical assessment of local tolerability, adverse event recording

Visit 3: Final study visit. Urine pregnancy test as applicable, clinical grading of signs and symptoms of TV, KOH test of TV-affected chest and back skin locations, scrub samples and samples for bacterial culture of IP and aqueous gel TV-affected anatomical locations, adverse

event recording, standard-of-care TV treatment may be provided at the discretion of the Investigator

Subjects enrolled to the multiple treatment dose groups:

Visit 0 (may be combined with Visit 1): Screening and enrollment visit, urine pregnancy test as applicable, KOH test of TV-affected chest and back skin locations

Visit 1: Baseline visit, clinical grading of signs and symptoms of TV, randomization of IP or vehicle gel to chest and back, scrub sample and bacterial culture of IP, aqueous gel, or vehicle gel TV-affected anatomical locations prior to first applications, application of IP, aqueous gel, or vehicle gel, adverse event recording

Visits 2, 3, 4: Clinical grading of signs and symptoms of TV, application of IP, aqueous gel, or vehicle gel per randomization to TV-affected locations, clinical assessment of local tolerability, adverse event recording

Visit 5: Clinical grading of signs and symptoms of TV, scrub sample and bacterial culture of IP, aqueous gel, or vehicle gel TV-affected anatomical locations prior to final applications, application of IP, aqueous gel, or vehicle gel, clinical assessment of local tolerability, adverse event recording

Visit 6: Final study visit. Urine pregnancy test as applicable, clinical grading of signs and symptoms of TV, KOH test of TV-affected chest and back skin locations, scrub sample and bacterial culture of IP, aqueous gel, and vehicle gel TV-affected anatomical locations, adverse event recording, standard-of-care TV treatment may be provided at the discretion of the Investigator

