6.4 Withdrawal or Termination

6.4.1 Subject Withdrawal

Participation in the study is strictly voluntary. A subject has the right to withdraw from the study at any time for any reason and is under no obligation to disclose the reason. If a subject withdraws, the Investigator and Sponsor are to be informed immediately and the withdrawal noted on the Case Report Form. Subjects may be replaced at the discretion of the Investigator and/or Sponsor only if both are in agreement.

The Investigator has the right to terminate participation of a subject at any time for any of the following:

- Use of non-permitted concomitant medication
- Lack of subject compliance
- Protocol violation
- Disease progression
- Any perceived safety risks

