6.4.2 Study Discontinuation

Study discontinuation is at the discretion of the Sponsor or the Investigator in any of, but not limited to, the following events:

- Occurrence of unusual AEs in terms of their nature, severity, causality, duration, or unexpected incidence.
- Medical or ethical reasons affecting the continued performance of the study.
- Difficulties in the recruitment of the subjects.

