6.4.3 Stopping Rules

The sponsor (Medical Director/Chief Medical Officer) will halt the study for a review of the safety data if there are safety concerns noted for any reason and if one or more subjects experience two AE's assessed as a Grade 3 (severe) or higher, of the same type that is considered possibly, probably or definitely related to the IP.

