6.9 Investigational Product

The IP, vehicle gel, or aqueous gel will be applied by study personnel at the investigative site at the baseline/Day 1 visit only for subjects receiving a single treatment dose, and once daily for 5

applications during the study for subjects receiving multiple treatment doses. Approximately 0.1 of the IP will be applied to a 100 cm² area of the TV-affected skin on the chest or back. The control location will be treated with 0.1ml of vehicle gel.

The doses for the three probiotic IP cohorts are 10^6 CFU/ ml, 10^8 CFU /ml, and 10^{10} CFU/ ml vs. vehicle gel.

It has been estimated that the density of bacteria on normal skin is approximately $1 \ge 10^{5}$ /cm². At our highest dose of 10^{10} CFU/ ml applying 0.1 ml to each 100 sq.cm. site will be adding $1 \ge 10^{10}$ CFU/cm² on chest or back.

The doses in this trial are comparable to the doses used in the study of other topical live bacterial products. An ammonia oxidizing bacterium has been used in Phase 2 trials to treat acne at a dose of 10^9 CFUs/ml (Whitlock 2017). In addition, a coagulase-negative *Staphylococcus* strain at a dose of $10^{7/}$ ml CFUs (Williams & Gallo, 2015) has been used in atopic dermatitis patients, and a strain of *P. acne* has been applied to the face of acne patients at a dose of $10^{8/}$ ml CFUs (NCT03450369).

Detailed information of the IP is included in the Investigator's Brochure (IB), provided separately.

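### After a safety signal, the rule for opening the next, 100-fold higher, dose cohort is ambiguous, and no outcome is given if the Investigator and sponsor disagree

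*Combined protocol and SAP*

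**What the plan says.** Escalation between dose cohorts is described in section 4.1.1 and, in nearly identical words, in the synopsis under Study Design/Type. Once the multiple-treatment subjects of a cohort have completed Day 14, local tolerability and adverse events are assessed. Two sentences then bear on the next cohort:

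- Without a signal: "If there are no safety signals, enrollment the next cohort will begin".
- With a signal: "If there are safety signals specific to local tolerability and AEs from either of the first two cohorts", then "the following dose escalating cohort may be not be enrolled if the Investigator and sponsor are in agreement".

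Section 6.9 sets the dose levels: "The doses for the three probiotic IP cohorts are 10^6 CFU/ ml, 10^8 CFU /ml, and 10^{10} CFU/ ml". Cohort 4 (vehicle gel vs. aqueous gel) lies outside this sequence; its "subjects may be enrolled before, in parallel with, or after the probiotic cohorts".

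Three provisions elsewhere are relevant:

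- Section 6.4.1, on replacement of withdrawn subjects: "Subjects may be replaced at the discretion of the Investigator and/or Sponsor only if both are in agreement". The same section lets the Investigator end a subject's participation for any perceived safety risk.
- Section 6.4.2: "Study discontinuation is at the discretion of the Sponsor or the Investigator".
- Section 6.4.3 has the sponsor halt the study for a safety review "if there are safety concerns noted for any reason and if one or more subjects experience two" related adverse events of the same type, Grade 3 or higher.

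**The concern.** In a dose-escalation study one expects a signal to hold the next dose until those responsible agree to go on. The sentence written for the signal case runs the other way: agreement is attached to withholding the dose, and even then withholding is only allowed. If one party wants to proceed and the other does not, the sentence gives no answer.

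Safety is a primary endpoint, and the product is a live organism. Section 2.1 reports its active ingredient as an opportunistic pathogen and lists local and systemic infection as possible but unlikely. The decision whether to raise the concentration after a signal should therefore not depend on how an unclear sentence is read.

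**Working it through.** The plan gives no figure to reproduce on this point. The check is a comparison of texts, with simple counts for scale.

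**1. The two escalation sentences, case by case**

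| Situation | No-signal sentence | Signal sentence | Cohort outcome stated? |
|---|---|---|---|
| No signal | Opens the next cohort | Does not apply | Yes: opens |
| Signal, both wish to withhold | Opening condition not met | Withholding permitted | In effect yes: withheld |
| Signal, both wish to proceed | Opening condition not met | Condition for withholding not met | No |
| Signal, parties disagree | Opening condition not met | Condition for withholding not met | No |

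The first sentence alone implies a hold after any signal. If that were the whole rule, the second sentence would have little to do: it has a function mainly if escalation after a signal remains possible. The text therefore points both ways in the last two rows.

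**2. Other decision wording.** For the lesser matter of replacing a subject, section 6.4.1 requires both parties to agree before acting. That is the form one would expect for escalation. It is a different decision, so this is a comparison of drafting and not a contradiction.

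**3. Do other provisions settle the open rows?**

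- Section 6.4.2: either party may act alone, but the action is to discontinue the study, not to withhold one cohort.
- Section 6.4.1: the Investigator may act alone, but subject by subject.
- Section 6.4.3: the trigger joins two conditions in a way that can mean both are needed or either is enough. Two illustrative signals show the difference:

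| Signal | Both conditions needed | Either enough |
|---|---|---|
| One related Grade 3 event | Not met | Met once noted as a safety concern |
| Grade 2 local reactions in 6 of 6 subjects | Not met | Met once noted as a safety concern |

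If the study is halted, no cohort opens during the review. What happens to the next cohort after the review is not stated.

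**4. Scale**

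Inputs: concentrations from section 6.9; cohort sizes 6, 6, 6 and 4 from Table 2; about 2 single-application and 4 multiple-application subjects per DBI-002 cohort from section 4.1.1.

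- Dose step: 10^8 / 10^6 = 100 and 10^10 / 10^8 = 100.
- Steps governed by the sentence: 2 (Cohort 1 to 2, Cohort 2 to 3).
- Subjects in the cohorts those steps open: 6 + 6 = 12. As a share of DBI-002 subjects, 12/18 = 67%; of all subjects, 12/22 = 55%.
- Subjects first exposed by one decision to open a cohort: about 2 of 6, one application each. The other 4 or so follow only if Day 5 shows no signals.
- Cohort 4 subjects lost if discontinuation is used in place of withholding a dose: at most 4, or 4/22 = 18%, and only if Cohort 4 has not started.

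**The case against.** The strongest reply is that the plan already implies a hold. The only sentence that opens a cohort requires the absence of signals, and no text authorises enrolling the next dose after one. The signal sentence is visibly garbled and may have been meant to cover joint cancellation of a later cohort. This stands in part: a reader might infer that the protocol directs escalation unless both parties agree to stop, and the documents do not support that. They support only that the rule is unclear and that the disagreement case is left open.

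A second reply is that a dissenting party can block escalation anyway. Either may discontinue the study under 6.4.2. The Investigator recruits from the Investigator's own practice (6.3), determines eligibility (6.5.1), may withdraw subjects for perceived risk (6.4.1) and is responsible for their safety (10.7). It is hard to construct from the documents a case in which an unwilling Investigator is made to dose the next cohort. This too stands, and it is why the practical risk is modest. But these powers work at the level of the study or the subject. Discontinuation is a blunt tool for withholding one dose, since it would also end any unfinished part of Cohort 4, which receives no probiotic.

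Third, a reader might take 12 of 18 as the number put at risk by one disputed decision. It is not: it counts everyone in the two cohorts that the sentence covers, and the single-application step limits first exposure to about 2 subjects.

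Finally, the change proposed leaves *signal* undefined and does not touch the step from single to multiple applications within a cohort, which has a no-signal condition but no rule for what follows a signal. Both remarks are correct. Neither is a reason to leave the cohort rule as it is.

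**Conclusion.** The concern holds as an ambiguity in a safety rule. The sentence written for the signal case makes joint agreement the condition for withholding a 100-fold higher dose and gives no outcome for disagreement. The no-signal sentence implies a hold but does not state one, and sections 6.4.1 to 6.4.3 do not supply one for the cohort.

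The rule covers two escalation steps. A single disputed decision would first expose about 2 subjects to one application each. The documents give no basis for how often a signal and a disagreement would coincide, so no probability can be attached. The conclusion rests on reading the sentence as written; if the drafters meant a hold, the text should say so. This should be corrected because the rule concerns safety and the correction costs almost nothing. The present wording does not show that subjects would in fact be escalated after a signal.

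**What to change.** In section 4.1.1 and in the synopsis, replace the sentence for the signal case with:

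*If there are safety signals, the next dose cohort will be held and will be enrolled only if both the Investigator and the sponsor agree in writing after review of the safety data; if they do not agree, it will not be enrolled.*

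The cost is one sentence in two places. It adds no visits, subjects or assessments and does not affect Cohort 4. The downside is a short documented pause, only when a signal occurs. What counts as a signal remains a judgement, as now.

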4.2 Study Endpoints

4.2.1 Primary Endpoint

a. Safety

Tolerability will be evaluated through assessment of TV disease state severity and signs and symptoms of local tolerability (pain/burning/stinging, pruritus, erythema, edema, and scabbing/crusting) at the application locations and review of adverse events.

b. Antimicrobial Efficacy

• Compare the change from baseline in quantity of *Malassezia species* based on molecular diagnostic quantitative polymerase chain reaction (qPCR) performed on samples collected from test sites at baseline prior to treatment at Days 5 and 14.

• Compare the change from baseline in the microbiome community and relative abundance of *Malassezia species* based on DNA sequencing performed on samples collected from test sites at baseline prior to treatment at Days 5 and 14.

4.2.2 Secondary Endpoints

- Proportion of samples at each time point in which *Malassezia species* can be detected by molecular diagnosis (qPCR).
- Proportion of samples at each time point in which the probiotic strain **can** be detected by molecular diagnosis (qPCR).
- Proportion of samples at each time point in which the probiotic strain **can** be detected by bacterial culture.
- Presence and abundance of live probiotic strain **abundance** on samples collected from test sites at baseline prior to treatment at Days 5 and 14. Not applicable to aqueous gel.
- Changes in the signs and symptoms of TV
- Change from KOH positive to KOH negative

4.2.3 Exploratory Endpoint

• Mean difference from baseline in individual signs and symptoms of TV at Days 5 and 14 between treatment groups and compared to baseline.

5 INVESTIGATIONAL PRODUCT (IP)

Table 2. Investigational Product and Aqueous Gel Cohorts, IP descriptions, and doses.

Cohorts	Investigational Product (IP)	Doses per Subject
Cohort 1: 6 subjects	Low dose 10 ⁶ CFUs /ml of DBI-002 probiotic vs. aqueous gel	Single treatment dose OR Once-daily application for 5 consecutive days
Cohort 2: 6 subjects	Medium dose 10 ⁸ CFUs /ml of DBI-002 probiotic vs. aqueous gel	Single treatment dose OR Once-daily application for 5 consecutive days
Cohort 3: 6 subjects High dose 10 ¹⁰ CFUs /ml of DBI-002 probiotic vs. aqueous gel		Single treatment dose OR Once-daily application for 5 consecutive days
Cohort 4: 4 subjects	Vehicle gel vs. aqueous (CMC) gel	Once-daily application for 5 consecutive days

6 ELIGIBILTY CRITERIA

6.1 Inclusion Criteria

Subjects must meet all of the following criteria to be included in the study:

- 1. Ability to understand, agree to and sign the study Informed Consent Form (ICF). If the subject is unable to provide consent him/herself, the subject's legally acceptable representative may provide written consent.
- 2. Male or Female Subjects of any race 18 65 years of age.
- 3. Subjects with a clinical diagnosis of Tinea versicolor (TV).
- 4. A positive potassium hydroxide (KOH) examination consistent with Malassezia prior to the treatment period done at the clinical site.
- 5. Agree to not use soap and water on the chest and back for at least 12 hours before the study visits for Baseline/Day 1, Day 5, and Day 14, and follow all study instructions for use of soap and water on the chest and back during participation in the study.

6.2 Exclusion Criteria

- 1. Females who are pregnant, planning a pregnancy, or breastfeeding.
- 2. Any dermatological conditions that could interfere with clinical evaluations or any disease state or physical condition which might expose the patient to an unacceptable risk by study participation.
- 3. Any underlying disease(s) or other dermatological conditions that require the use of exclusionary topical or systemic therapy (see below).
- 4. Known sensitivity to any of the components of the study medication.
- 5. Use of a prescription or nonprescription topical treatment on the targeted lesions TV anatomical locations within the previous 4 weeks, for example: anti-fungal, antibacterial or anti-microbial products, selenium and anti-inflammatories (e.g. corticosteroids).
- 6. Use of a systemic anti-fungal or anti-bacterial treatment for TV within the previous 4 weeks.
- 7. Use of medicated shampoos and/or soaps within the previous 4 weeks.
- 8. Treatment of any type of cancer within the last 6 months.
- 9. History of any significant internal disease which contraindicates use of live microbiome (e.g. leukemia, liver failure, cardiovascular disease).

- 10. Subjects who are known to be allergic to any of the test product(s) or any components in the investigational product(s) or history of hypersensitivity or allergic reactions to any of the study preparations as described in the Investigator's Brochure (IB).
- 11. AIDS or AIDS related complex by medical history.
- 12. Known or suspected to be taking immunosuppressive medications and/or has a known or suspected autoimmune disease.
- 13. Any subject not able to meet the study attendance requirements.
- 14. Subjects who have participated in any other trial of an investigational drug or device within 30 days prior to enrollment or participation in a research study concurrent with this study.

